3.2.4 Sample size calculation

Sample size is based on power analyses on the expected changes in the primary outcome 'walking efficiency'.

Walking efficiency, assessed with a portable gas-analysis system, will be defined as the EC of walking $(J^{-1} \cdot kg^{-1} \cdot m^1)$. Based on previous research, EC of walking in children with CP is

shown to be 30-50% higher, compared to healthy children (10-12). CP children with GMFCS levels I and II show a mean net EC of walking of 5.02 (±1.70) J⁻¹·kg⁻¹·m¹ (29). Based on previous research on the effectiveness of AFOs of children with CP (28;29), a reduction of 25% from this value (\approx 1.26 J⁻¹·kg⁻¹·m¹) is chosen as a clinical significant change. Based on these values, a standardized difference for within-subject studies can be calculated using the following formula: N = 2SD² (Z α + Z β)²/ Δ^2 (59). Assuming a power of 80% and a significance level of 0.05, a sample size of 29 patients is needed to detect a difference of 25% in net EC of walking. A sample size of 32 is chosen to allow for dropout and for a sufficient sample for regression analysis.

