3.5.2 Withdrawal of individual subjects

Subjects can leave the study at any time for any reason if they wish to do so without any consequences. The investigator can decide to withdraw a subject from the study for urgent medical reasons.

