3.5.3 Replacement of individual subjects after withdrawal

Withdrawn subjects will not be replaced.

3.5.4 **Premature termination of the study**

The study will only be terminated prematurely for urgent medical or other urgent reasons. In this case only possibly collected data will be analysed.

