3.6 Statistical analysis

All statistical analyses will be done with SPSS.

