3.6.2 Univariate analysis

To analyse differences in AFO efficacy between AFO configurations, means of primary and secondary outcome measures at $T1_{K1}$, $T1_{K2}$, and $T1_{K3}$ will be compared using a repeated measures ANOVA.

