3.6.3 Multivariate analysis

Evaluation of efficacy of the subject's optimal AFO will be based on analyses of pre/postintervention differences in primary and secondary outcome measures. Means of baseline measurements (T0) will be compared to evaluation measurements (T1_K) and long-term follow-up measurements (T2_{Kopt}) using a Linear Mixed Model (LMM) for repeated measures¹.

Multivariate linear regression analyses will be applied to investigate what changes in the secondary outcome measure 'biomechanics of gait' are associated with changes in primary outcome measures 'walking efficiency' and 'daily activity'. First, a stepwise univariate regression (ANOVA) will be performed to determine which factors are significantly associated with changes in biomechanics of gait. Next, significant factors will be analysed in a multivariate regression analysis model.

Multivariate regression analysis will also be applied to investigate to what extent the child characteristics and AFO properties provide determinants for success of treatment with AFOs. First, a stepwise univariate regression (ANOVA) will be performed to determine which factors are significantly associated with outcome of AFO treatment. Significant factors will be inculded in a multivariate regression model. Factors that will be analysed in the model will include baseline motor impairements, GMFCS level, gait pattern, EC of walking, physical fitness level, and AFO stiffness and neutral anlge.

¹ Participation measures (assessed with the CAPE) will only be done at baseline (T0) and at long-term follow-up (T2). Assuming that data are normally distributed, means of this outcome measure will be compared using paired samples t-test.

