APPENDIX A. Policy for handling complaints regarding the investigational AFO

When the new AFO is delivered, patients will be instructed to wear the orthosis during an accommodation period. This accommodation period is constructed in a way that the time of wearing the AFO during the day is gradually extended, in order to minimalize the risk of developing problems (e.g. pressure sores). In addition, parents will be instructed to carefully check for pressure sores on the legs or feet of their child and they are instructed to contact the investigator if any problems or complaints occur during the accommodation period.

A standard policy for handling complaints will be followed for each patient (figure 2). Patients will be contacted one week after delivery of each new AFO to check if there are any complaints (adverse events), like pain, discomfort, or pressure sores. If the patient has no complaints, the accommodation period will continue until the next visit is scheduled.

If the patient does experience problems, the investigator will identify these problems and decide which steps need to be taken:

a) For fitting problems like pain or pressure sores, the patient will be directed to the orthotist as soon as possible, in order to adjust the AFO. These fitting problems are common in orthotic care when prescribing a new AFO and can generally be resolved.

b) For gait related problems that are unacceptable for the patient (e.g. frequent falls or extreme fatigue during walking), the investigator will invite the patient to visit the medical center. At the medical center, the investigator will check if any changes in AFO configuration (i.e. neutral angle) can resolve the problem.

After each attempt to resolve a problem, either fitting of gait related, the investigator will contact the patient by phone after several days to check if problems are resolved. If any new problems are present or problems recurred, the investigator will follow the described complaint policy again. For persisting gait-related problems that are unacceptable for the patient, the investigator might decide to end the accommodation period of that AFO configuration and do follow-up measurements immediately. Subsequently, the patient will continue to the next AFO configuration. When problems are resolved, the accommodation period will continue until the next measurement moment is scheduled.

[figure not shown]

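### The stiffness comparison in 3.6.2 discards usable T1 values because it relies on a complete-case repeated measures ANOVA, although the mixed model planned in 3.6.3 would keep them at almost no cost

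*Protocol*

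**What the plan says.** Section 3.6.2 gives one method for comparing the rigid, stiff and flexible configurations: "To analyse differences in AFO efficacy between AFO configurations, means of primary and secondary outcome measures at" the three T1 evaluations "will be compared using a repeated measures ANOVA". This covers every primary and secondary outcome collected at T1, namely energy cost, step-monitor activity, gait biomechanics and walking speed. Section 3.6 fixes the software: "All statistical analyses will be done with SPSS". No rule for incomplete T1 data accompanies the comparison.

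Section 3.6.3 names a different method for the comparison of T0, T1 and T2, "using a Linear Mixed Model (LMM) for repeated measures", and that model takes in the same T1 measurements.

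Four other places bear on whether T1 values will be complete:

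- Section 3.5.2: "Subjects can leave the study at any time for any reason if they wish to do so without any consequences".
- Section 3.5.3: "Withdrawn subjects will not be replaced".
- Section 3.2.4, after deriving 29 children: "A sample size of 32 is chosen to allow for dropout" and to support the regression analysis.
- Appendix A, for persisting unacceptable gait problems: "the investigator might decide to end the accommodation period of that AFO configuration and do follow-up measurements immediately". The child then moves on to the next configuration. The notes to Table 2 in section 3.4 place the step-monitor recording in the week before the visit.

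**The concern.** The standard SPSS repeated measures ANOVA takes one row per child and removes the row if any of the three values is absent. A child measured in two configurations then adds nothing for that outcome, not even to the contrast between those two configurations. The child is lost only from this comparison and this outcome, and remains in the study and in the 3.6.3 model.

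Missing values are foreseeable. Each child goes through three consecutive periods of four to eight weeks, may leave at any point and is not replaced. A configuration that ends early leads to an immediate visit, which may come before a full week of step-monitor data has been collected, and daily activity is a primary outcome.

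At stake is the precision of the only comparison that uses the randomised order of configurations, in a sample of 32. The plan also already holds a method that avoids the loss, so two analyses of the same T1 data could rest on somewhat different sets of children without need.

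**Working it through.** **1. The plan's own figure.** Section 3.2.4 gives SD 1.70, a difference of 1.26 (25% of 5.02), 80% power and a significance level of 0.05, with N = 2·SD²·(Zα+Zβ)²/Δ². Taken two-sided:

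2 × 1.70² × (1.960 + 0.842)² / 1.26² = 28.6, rounded up to 29.

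The stated 29 is reproduced. Enrolling 32 leaves 3 children, or 3/32 = 9.4%. The 29 was derived for a 25% change in energy cost and not for the three-configuration contrast, so it serves here only as a benchmark.

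**2. Complete children.** The protocol gives no missing rate. Let m be the assumed probability that a T1 value is missing at a visit or, for withdrawal, that the child leaves before that visit. Either way the expected number with all three values is 32(1−m)³:

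- m = 3%: 29.2
- m = 5%: 27.4
- m = 10%: 23.3

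**3. What the ANOVA discards.** This depends on the pattern of gaps. At m = 5%:

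- *Intermittent gaps (independent between visits).* Children with two of three values: 3 × 32 × 0.95² × 0.05 = 4.3. With one: 3 × 32 × 0.95 × 0.05² = 0.2. Observed values discarded: 2 × 4.33 + 0.23 = 8.9.
- *Withdrawal (monotone).* Children with no T1 value: 32 × 0.05 = 1.6. With one: 32 × 0.95 × 0.05 = 1.5. With two: 32 × 0.95² × 0.05 = 1.4. Observed values discarded: 1.52 + 2 × 1.44 = 4.4. Only the 1.4 children with two values add much to a within-child contrast, so a mixed model recovers less here.

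**4. Variance of a pairwise stiffness contrast.** With k complete children and within-child correlation ρ, the complete-case variance is 2·SD²·(1−ρ)/k. The comparator is generalised least squares on all available values with the same compound-symmetric covariance, averaged over simulated missingness patterns in 32 children. Assumptions: SD 1.70 and ρ between 0.5 and 0.8. Adding period terms leaves the ratios almost unchanged.

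| Assumed m | Complete of 32 | Discarded, withdrawal | Excess variance, withdrawal | Discarded, intermittent | Excess variance, intermittent |
|---|---|---|---|---|---|
| 3% | 29.2 | 2.7 | about 2% | 5.5 | about 5% |
| 5% | 27.4 | 4.4 | 3–4% | 8.9 | about 9% |
| 10% | 23.3 | 8.1 | 7–9% | 16.4 | about 19% |

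On the standard-error scale the excess is about half as large: √1.02 = 1.01 at the low end and √1.19 = 1.09 at the high end. With 10% intermittent gaps and ρ = 0.5, for example, the standard error is 0.354 for complete cases and 0.323 for the mixed model.

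**5. Bias.** In a simulation where children left after a poor period, the complete-case contrast averaged 0.485 against a true 0.50. In that scenario the bias was small.

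**The case against.** The strongest reply is that the loss is small on the only route to missing values that the protocol states outright. Withdrawal is monotone, and a child with no T1 value adds nothing to either method, while a child with one adds almost nothing to a within-child contrast. At about the three losses that separate 32 from 29, the excess variance is near 2%. This stands, and it is why the withdrawal figures are given alongside the larger ones. Intermittent gaps, such as a lost step-monitor week or a failed walking test, are plausible, but their frequency is unknown.

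A reader might infer that the children removed are mainly those who tolerated a configuration badly, so that the comparison drifts towards children who coped with all three. The documents do not support that. When a configuration is ended early, Appendix A has the measurements taken at once, which is meant to yield a T1 value, and the bias simulation showed little effect.

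Two further replies have partial force. Sections 3.6.2 and 3.6.3 answer different questions, and section 3.5.1 selects the optimal AFO once all configurations have been evaluated, so the two analysis sets should largely overlap. The mismatch is therefore minor.

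Missing-data rules are also often left to an analysis plan, and this protocol does not exclude imputation. But the ANOVA is fixed in the protocol, next to a section that names a mixed model for a different comparison, so the choice of method can fairly be questioned here.

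**Conclusion.** The point holds as a matter of efficiency. The method fixed in 3.6.2 would, in its standard SPSS form, discard observed T1 values that the model in 3.6.3 would use. At an assumed 3% to 10% missing per T1 visit, this inflates the variance of a pairwise stiffness contrast by about 2% to 9% under withdrawal alone, and by about 5% to 19% if gaps are intermittent. These figures rest on the assumed missing rates, SD 1.70, within-child correlation of 0.5 to 0.8 and compound symmetry.

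Selection bias cannot be ruled out, but nothing in the document demonstrates it. Nor does a fall below 29 complete children amount to a power failure for this comparison, since the 29 was not calculated for it. The planned ANOVA remains a valid analysis when the data are complete.

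**What to change.** In section 3.6.2, replace the repeated measures ANOVA with the linear mixed model already named in 3.6.3, fitted to all available T1 values of each outcome. Use configuration and period as fixed effects and child as a random effect. Period belongs in the model because the order of configurations is randomised over six sequences (section 3.1.1). Report for each outcome how many children contribute one, two and three configurations, and give the complete-case ANOVA as a sensitivity analysis.

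The cost is a few lines of analysis text, with no new software, data or visits. The downside is reliance on missing at random: the model does not correct for values that are missing because a configuration was intolerable. The report should say so and list the reasons for missing T1 values.

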3.6.3 Multivariate analysis

Evaluation of efficacy of the subject's optimal AFO will be based on analyses of pre/postintervention differences in primary and secondary outcome measures. Means of baseline measurements (T0) will be compared to evaluation measurements (T1_K) and long-term follow-up measurements (T2_{Kopt}) using a Linear Mixed Model (LMM) for repeated measures¹.

Multivariate linear regression analyses will be applied to investigate what changes in the secondary outcome measure 'biomechanics of gait' are associated with changes in primary outcome measures 'walking efficiency' and 'daily activity'. First, a stepwise univariate regression (ANOVA) will be performed to determine which factors are significantly associated with changes in biomechanics of gait. Next, significant factors will be analysed in a multivariate regression analysis model.

Multivariate regression analysis will also be applied to investigate to what extent the child characteristics and AFO properties provide determinants for success of treatment with AFOs. First, a stepwise univariate regression (ANOVA) will be performed to determine which factors are significantly associated with outcome of AFO treatment. Significant factors will be inculded in a multivariate regression model. Factors that will be analysed in the model will include baseline motor impairements, GMFCS level, gait pattern, EC of walking, physical fitness level, and AFO stiffness and neutral anlge.

¹ Participation measures (assessed with the CAPE) will only be done at baseline (T0) and at long-term follow-up (T2). Assuming that data are normally distributed, means of this outcome measure will be compared using paired samples t-test.

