Baseline measurements with intervention AFO (visit IV, V, and VI)

During the period that the AFO configuration is worn, subjects will also wear the SAM for one week. After wearing the first intervention AFO-FC, subjects will come to the medical center for the evaluation measurements (T1_K). During this visit, 3D-gait analysis and ECWT will be performed, and the FMS and FAQ will be completed. The researcher will ask both the child and parent(s) to rate the worn AFO in terms of satisfaction. Then, properties of the new AFO configuration will be determined and the second AFO-FC will be tuned. Only during visit IV (T1K1), a 3D-gait analysis with the new configuration (K2) will be performed directly,to measure the immediate biomechanical effects of the AFO. The subject will wear the second AFO-FC for four to eight weeks (acclimation period will be matched according to total time that the first AFO-FC is worn), after which the same evaluation measurements will be done (including SAM). The motivation diary will be kept until the next visit to the medical center. This time schedule and set of measurements will be repeated for the third AFO-FC.

Optimal AFO selection (visit VI)

When the short-term follow-up measurements for all AFO configurations are completed, data will be analyzed and the subject's most optimal AFO will be selected. Selection of the subject's optimal AFO will be based on data of gait analysis (primarily on the knee angle in midstance), ECWT, and degree of satisfaction of the child and parent(s). Subsequently, the

Neuro Swing[®] ankle joint system of the subject's AFO-FC will be configured according to what is considered as optimal.

Long-term follow-up measurements (visit VIII)

The subject will wear the optimal AFO-FC during a period of twelve to twenty weeks, to ensure full habitation before long-term follow-up measurements will be performed ($T2_{kopt}$). Measurements at $T2_{kopt}$ will include the CAPE and SAM (of which data will be assessed during the week prior to the visit), adherence (data with the @monitor (83) will be assessed two weeks prior to the visit), 3D-gait analysis, ECWT, FAQ, FMS, and GAS.

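### Section 3.6.3 judges the optimal AFO partly on T1, the data used to choose it: depending on which T1 value enters, the T0–T1 contrast is either selection-biased or does not estimate the optimal AFO's effect

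*Protocol*

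**What the plan says.** Selection is described in Protocol 3.5.1, under the optimal AFO selection visit: "Selection of the subject's optimal AFO will be based on data of gait analysis (primarily on the knee angle in midstance), ECWT", with the satisfaction of child and parents as the remaining input. No weights are given. Section 3.1.1 places this choice after all three T1 evaluations.

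Evaluation is described in 3.6.3: "Evaluation of efficacy of the subject's optimal AFO will be based on analyses of pre/postintervention differences in primary and secondary outcome measures". The next sentence begins "Means of baseline measurements (T0) will be compared to evaluation measurements" and names T1_K, followed by T2_Kopt, in a linear mixed model.

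Energy cost from the walking test is a primary outcome (3.4.1) and the basis of the sample size (3.2.4). Gait biomechanics is a secondary outcome (3.4.2). Both therefore help choose the AFO and are then listed as evidence of its efficacy. Neither section mentions this overlap.

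The comparison among the three stiffness levels has its own section, 3.6.2, which uses all three T1 measurements by repeated measures ANOVA.

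**The concern.** When the best of three noisy measurements is picked, the winner is favourable partly because its measurement error happened to be favourable. If that same measurement is then compared with baseline, the error is counted as treatment effect, and a gain appears even when the three configurations are identical and none differs from baseline. A fresh measurement at T2 does not carry that error, so the same amount reappears as an apparent decline from T1 to T2.

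Two conclusions are at stake for energy cost and the gait variables: how large the short-term benefit of the individually chosen AFO is, and whether it lasts to long-term follow-up.

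**Working it through.** **Which T1 value enters.** Table 1 defines T1 as the follow-up for each configuration, and the note to Table 2 says T1 is repeated for each. Section 3.6.3 writes T1_K in a paragraph about the optimal AFO and does not say whether K is all three or the chosen one.

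- Reading A, the chosen configuration only: selection bias, sized below.
- Reading B, all three unselected: no selection bias, but the T0–T1 contrast averages in two configurations that were not chosen.

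**Inputs from 3.2.4.** "mean net EC of walking of 5.02 (±1.70" for mean and SD; a target of "a reduction of 25% from this value", about 1.26 J/kg/m; "Assuming a power of 80% and a significance level of 0.05".

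The plan's own figure reproduces with two-sided alpha: N = 2 × 1.70² × (1.960 + 0.842)² / 1.26² = 28.6, hence 29, with 32 planned. The protocol gives no figure for selection bias and no within-child SD.

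**Assumptions needed.** Let rho be the test-retest correlation of energy cost, so that the within-child error SD is 1.70 × √(1 − rho). Let r be the correlation between the selection score and the energy cost error. The documents give neither, so a range is shown.

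**Formula.** For three independent equal normal values, the expected minimum lies 3/(2√π) = 0.846 SD below the mean. With no true effect, the bias in T0 versus the chosen T1 is r × 0.846 × error SD.

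**Reading A results.** Simulation of 10,000 trials with n = 32, no true effect and three equal configurations. Entries are the spurious reduction in J/kg/m, with its share of the 1.26 target in brackets.

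| rho | error SD | r = 1 | r = 0.5 | r = 0.3 |
|---|---|---|---|---|
| 0.5 | 1.20 | 1.019 (81%) | 0.508 (40%) | 0.306 (24%) |
| 0.8 | 0.76 | 0.646 (51%) | 0.321 (25%) | 0.194 (15%) |
| 0.9 | 0.54 | 0.455 (36%) | 0.229 (18%) | 0.138 (11%) |
| 0.95 | 0.38 | 0.323 (26%) | 0.161 (13%) | 0.098 (8%) |

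Check by formula at rho = 0.8, r = 0.5: 0.5 × 0.846 × 0.76 = 0.32.

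A paired t-test of T0 against the chosen T1 at two-sided 0.05 rejects in about 96% of trials at r = 1, 39% at r = 0.5, 17% at r = 0.3 and 5% at r = 0. These rates do not depend on rho, because bias and error SD scale together. The mean T1-to-T2 change is the same amount in the other direction (at rho = 0.8: 0.645 for r = 1, 0.320 for r = 0.5).

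T0 versus T2 shows a bias of about 0 and rejects in 4.4% to 5.5% of trials in every scenario. T0 versus the unselected mean of all three T1 values also rejects in about 5%.

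**If configurations truly differ.** With an assumed SD of 0.6 between configurations, rho = 0.8 and r = 1, the chosen T1 value shows an average gain of 0.82, of which 0.31 is real and 0.82 − 0.31 = 0.51 comes from selection. In the same scenario the average over all three configurations shows no gain, so Reading B misses the real 0.31.

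**The case against.** The strongest counter-argument is that Reading A is not stated. The protocol uses the subscript K generically, writes Kopt where it means the chosen configuration (in the same sentence of 3.6.3), and never uses a T1 symbol for the chosen one. This stands: a reader might infer that 3.6.3 definitely analyses the winner's T1 value, and the text does not establish that. It does not remove the problem. The paragraph concerns the optimal AFO, the unselected comparison already sits in 3.6.2, and under Reading B the T0–T1 contrast answers a different question.

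A reader might also infer that any loss from T1 to T2 is regression to the mean. The documents do not support this. Section 3.6.3 states no T1–T2 contrast, and real change could contribute; 3.1.1 itself names weather as affecting activity and participation. Only part of a decline can be put down to selection.

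The size is also open to challenge. Selection rests primarily on midstance knee angle, so the r = 1 column is an upper bound for energy cost, and three equal configurations is the extreme case. Both points stand.

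Finally, ranking contrasts is often left to an analysis plan, which is not at hand. Here, however, the protocol itself lists T1 as part of the efficacy comparison for the optimal AFO.

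**Conclusion.** The concern holds in a limited form. Section 3.6.3 should not offer T0 versus T1_K as evidence of the optimal AFO's efficacy: under one reading the contrast is biased towards benefit for energy cost and gait, and under the other it does not estimate that AFO's effect.

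Under Reading A the energy cost bias is at most 0.85 within-child error SD, and about 0.42 SD or less if r is 0.5 or less. Over the assumed rho of 0.5 to 0.95, r = 0.5 gives 0.16 to 0.51 J/kg/m, or 13% to 40% of the 1.26 target. These figures rest on assumed values of rho and r and on equal configurations; the protocol does not determine them.

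The scope is limited to outcomes used in selection. Daily activity from the step monitor, the other primary outcome, is not a listed criterion and is affected only if its T1 error correlates with those criteria. Participation (CAPE) has no T1 value and is unaffected. Efficacy can still be assessed, because T0 versus T2_Kopt is already in the plan and is free of this particular bias.

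**What to change.** In 3.6.3:

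- Name T0 versus T2_Kopt as the efficacy contrast for the optimal AFO. The footnote to 3.6.3 already does this for participation.
- State that T1 data enter for all three configurations, unselected, both for the stiffness comparison in 3.6.2 and for short-term T0 versus T1 effects per configuration. A ban on all other T1 use would go too far, since unselected T0–T1 contrasts do not carry this bias.
- If the chosen configuration's T1 value is compared with T0 or T2 on energy cost or gait, label that comparison descriptive and subject to selection bias.

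This takes two or three sentences; visits, measurements and sample size are unchanged. The downside is that children who leave before T2 contribute less to the efficacy contrast. Withdrawn children are not replaced (3.5.3), and the margin over the calculated size is 32 − 29 = 3 children, which 3.2.4 also assigns to the regression analysis: "A sample size of 32 is chosen to allow for dropout and for a sufficient sample for regression analysis".

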The primary objective of this study is to evaluate AFO efficacy in children with spastic CP on the ICF components 'body functions and structures' (i.e. biomechanics of gait) and 'activities and participation' (i.e. walking efficiency and frequency of participation).

The main research question related to this objective is: 1) what are the effects of wearing a specific AFO on biomechanics of gait, walking efficiency, daily activity and frequency of participation in children with spastic CP, whose gait is characterized by a flexed knee pattern? An additional research question is: 1a) what biomechanical changes of gait, resulting from wearing the AFO, lead to an improved walking efficiency, increased daily activity and/or frequency of participation in this specific patient group?

Secondary objective:

The secondary aim of this study is to identify prognostic factors for either a successful or unsuccessful outcome of AFO treatment on activities and participation (i.e. walking efficiency, daily activity and frequency of participation) in children with spastic CP.

The main research question for this objective is: 2) can we identify prognostic factors for a successful or unsuccessful outcome on walking efficiency, daily activity and frequency of participation after AFO treatment in children with spastic CP, whose gait is characterized by flexed knee pattern? Additional questions are: 2a) how do AFO properties (e.g. stiffness) influence the patient's gait biomechanics?; and 2b) what is the effect of gait improvements, as a result of AFO stiffness optimization, on daily activity and frequency of participation?

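### The mechanism regression screens on gait biomechanics, its own explanatory side; the prognostic regression leaves the role of baseline energy cost open and rests on a sample-size claim with no calculation behind it

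*Protocol*

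**What the plan says.** Section 3.6.3 of the Protocol describes two regressions.

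- **Mechanism regression.** It looks for the biomechanical changes that "are associated with changes in primary outcome measures", namely walking efficiency and daily activity. This serves research question 1a, which asks "what biomechanical changes of gait, resulting from wearing the AFO, lead to an improved walking efficiency" (and more activity or participation). The screening sentence then reads: "First, a stepwise univariate regression (ANOVA) will be performed to determine which factors are significantly associated with changes in biomechanics of gait". Factors that pass go into the multivariable model.
- **Prognostic regression.** It serves the secondary objective. Its screen is to "determine which factors are significantly associated with outcome of AFO treatment", and again only significant factors go forward. The candidate list begins: "Factors that will be analysed in the model will include baseline motor impairements, GMFCS level, gait pattern, EC of walking". Physical fitness, AFO stiffness and neutral angle complete it, so seven factors are named.

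The secondary objective names walking efficiency, daily activity and participation as the outcomes to be predicted, and section 3.2.4 defines walking efficiency as EC. On numbers, that section says: "A sample size of 32 is chosen to allow for dropout and for a sufficient sample for regression analysis". Section 3.5.3 rules out replacement of withdrawals, so 32 is a ceiling.

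**The concern.** In question 1a, biomechanics explains and EC and activity respond. A screen that keeps whatever is associated with biomechanics treats the explanatory variable as the response. An analyst who followed it literally could select and fit a model that does not answer 1a.

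In the prognostic regression, EC appears to stand on both sides for the walking-efficiency outcome. If outcome means change from baseline, baseline EC is part of the outcome, and a negative association arises without any real difference in response. The report could then say that children with high EC benefit most when nothing of the kind is true.

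Finally, significance screening of seven factors in about 30 children is fragile, and the Protocol asserts that the sample suffices without showing it. The introduction hopes that these determinants will help to build a framework for AFO management, so a false predictor could carry weight.

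**Working it through.** **1. Screening target (no arithmetic).**

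| | Aim | Screen is against |
|---|---|---|
| Mechanism regression | biomechanical change as explanation of change in EC and activity | change in biomechanics |
| Prognostic regression | child and AFO factors as explanation of treatment outcome | treatment outcome |

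The second row is consistent and the first is not.

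**2. What the sample size was calculated for.** Section 3.2.4 gives SD 1.70, difference 1.26 (25% of 5.02), power 80%, alpha 0.05 and N = 2·SD²·(Zα+Zβ)²/Δ². Two-sided:

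N = 2 × 1.70² × (1.960 + 0.842)² / 1.26² = 28.6, rounded up to 29.

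The Protocol's 29 is reproduced. It concerns a mean difference in EC. The step to 32 adds three children for dropout and regression together, and no regression calculation is shown. Seven factors in 32 children is 32/7 = 4.6 children per factor.

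**3. Baseline EC against change in EC.** Assumptions: equal variances at baseline and follow-up, correlation ρ between them, and no differential response beyond that correlation. Then corr(baseline, change) = −√((1−ρ)/2). The Protocol gives no ρ, so a range is shown. Rejection rates (two-sided 0.05) come from 40,000 simulated trials per setting.

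| assumed ρ | corr(baseline, change) | significant, n=32 | significant, n=29 |
|---|---|---|---|
| 0.7 | −0.39 | 61% | 56% |
| 0.8 | −0.32 | 43% | 39% |
| 0.9 | −0.22 | 23% | 22% |

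If the outcome is follow-up EC instead, baseline EC is significant in over 99% of trials for each of these ρ, because EC tracks over time. That says nothing about response to the AFO.

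**4. Significance screening.** Assumptions: seven independent factors, none related to the outcome, each tested at 0.05 (section 3.6.3 states no level for the screen). P(at least one passes) = 1 − 0.95⁷ = 0.30 per outcome. Simulation at n=32 also gives 0.30. The screen is weak in the other direction too: at n=32 only |r| of about 0.35 or more passes, and a true correlation of 0.3 is detected about 38% of the time.

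**The case against.** *The screening sentence is a drafting slip.* Probably so: the sentence before it states the right aim. A univariable association is also symmetric, so if the undefined 'factors' are the EC and activity changes, the same pairs would be selected whichever is called dependent. This stands for the screen. It does not extend to the multivariable model, where the choice of dependent variable changes what is estimated. The sentence still has to be corrected.

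*Coupling is conditional.* This stands. Section 3.6.3 bases efficacy on pre-post differences but does not say that success is scored as change. The coupling touches only the walking-efficiency outcome. The word 'baseline' precedes motor impairments in the list, so baseline EC is an inference, though the only sensible one for a prognostic factor. Once baseline EC is in a linear model, change and follow-up EC as outcome give identical coefficients for every other factor, and only the EC coefficient shifts, by 1. The exposure is therefore the univariable EC screen and the reading of that one coefficient.

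*The choice among small-sample regression methods is a preference.* This stands. Penalised regression or a particular number of factors is not something the Protocol gets wrong by omitting.

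A reader might also infer larger figures. Counting parameters instead of factors gives nine tests and 1 − 0.95⁹ = 37%, but an ANOVA screen gives one p-value per factor and seven are named. An expected R² of 9/31 = 0.29 under the null belongs to a full nine-parameter model, which this plan does not fit.

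**Conclusion.** The point holds in three parts of unequal strength.

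- The mechanism regression's screening rule contradicts its stated aim and question 1a. This rests on the text alone.
- For the walking-efficiency outcome, baseline EC would be flagged by coupling alone in roughly 23% to 60% of null trials at n=32. This is conditional on success being scored as change, and on the assumed correlations of 0.7 to 0.9 with equal variances.
- Screening the seven factors passes at least one null factor in about 30% of trials per outcome, assuming independent factors and a 0.05 level. The sufficiency claim has no calculation behind it.

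Two stronger readings are not supported. One is that the whole regression plan screens on the wrong variable: the prognostic regression screens against treatment outcome. The other is that screening alone makes spurious predictors more likely than not: 30% per outcome does not show that. The efficacy comparison by linear mixed model is unaffected.

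**What to change.** 1. **Mechanism regression.** Reword section 3.6.3 so that change in EC and change in daily activity are the dependent variables and biomechanical changes are related to them, preferably from a short pre-named list. Note that midstance knee angle and the ECWT also help to select the optimal AFO (section 3.5.1), so their association at T2 may be shaped by that selection.
2. **Prognostic regression, walking efficiency.** Define success. Model T2 EC with baseline EC always included as a covariate, outside the screen, and do not interpret its coefficient as a prognostic factor for response.
3. **Status.** Label the prognostic results exploratory, and delete from section 3.2.4 the statement that the sample is sufficient for regression.

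The cost is wording only, with no change to visits, measurements or recruitment. The downside is that fewer factors can be claimed as predictors.
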